Additionally, we will review prison logs and health records to determine how many patients are diagnosed with TB and HIV, start TB and HIV treatment, and the time to treatment initiation and completion (for TB only) among non-study patients to compare with outcomes study patients. We will abstract data from prison logs without identifiers and will not interact with incarcerated individuals other than the study participants. Additional structural non-patient data pertaining to service delivery, implementation of HIV guidelines, and operations in the prison may also be collected to compare prison HIV and TB care to national and global guidelines (ex. number of medical staff, whether diagnostic or monitoring tools (ex. HIV viral load), medications available on the prison formulary, etc) are available.

Eligibility for Part A includes:

- 1) Age \geq 18 years
- 2) Malaysian citizen
- 3) Prison sentence \geq 3 months
- 4) Absence of active TB within past 2 years of enrollment
- 5) Newly admitted prison inmate (<2 days)
- 6) Able to provide informed consent

Part B: Prisoners with LTBI from Aim 1 will be asked to participate in **Part B**. Our preliminary data suggest that >80% of all prisoners have TST+ and 94% of HIV+s and 63% of HIV-s are HCV Ab+.^{10,12,13} We have documented both in a systematic review and using empiric data in Malaysia that few prisoners with LTBI receive preventive TB therapy and for those that do, the major factor contributing to treatment non-completion is release from prison and hepatotoxicity.¹⁹ Consequently, WHO provides conflicting guidance on TB preventive therapy in prisoners. In its guidelines on managing TB in closed settings, preventive therapy is not recommended, yet in its HIV treatment guidelines, long-term isoniazid preventive therapy is recommended, especially if TST+. Since these recommendations, a large RCT among non-prisoners compared a once-weekly 12-week regimen of INH/rifapentine (12HR) to daily 26 weeks of isoniazid preventive therapy (IPT: 26H). In terms of TB prevention, efficacy was similar, but patients prescribed short-course 12HR had higher treatment completion rates (82.1% v. 69.0%; p<0.001).²⁰ Since shorter LTBI preventive strategies are likely to improve completion, perhaps overturning previous recommendations based on the best science. A remaining concern, however, is the high prevalence of PWIDs with chronic HCV infection in prison, which might increase hepatotoxicity

[figure not shown]

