in a 12HR combination since both isoniazid and rifapentine can damage the liver; CDC is calling for studies of 12HR in prisoners, but have not yet funded research. In the absence of studies of 12HR use in prisoners, it is crucial to assess both completion rates and tolerability (especially when high HCV prevalence is present).

Eligibility for Part B includes:

- 1) Meets inclusion criteria for Part A
- 2) Has latent TB (HIV+, or TST \geq 10mm (HIV-)) and no active TB disease
- 3) \geq 6 months before end of sentence to ensure option for treatment completion
- 4) AST/ALT <5 ULN, or AST/ALT <3 x ULN if TBil >2 x ULN
- 5) Not on a protease inhibitor (drug interaction with rifapentine)
- 6) No known porphyria
- 7) Not pregnant (women only).

Enrolled participants will undergo block stratified randomization, stratifying on four factors: a) CD4 <350 (if HIV+); b) HCV Ab status; c) ART status; and d) opioid dependence. After randomization and allocation to 12HR or 26H, participants will be provided 12HR weekly (12 weeks) and 26H daily (26 weeks) as directly observed therapy. Every 4 weeks, patients will be monitored for AST/ALT, adverse side effects and pregnancy. Premature treatment discontinuation will occur for any DAIDS Grade 4 toxicity, patient refusal to continue, or pregnancy (women only).

Study Design: TB Studies

Legend: LTBI=latent TB infection; H=isoniazid; HP=isoniazid + rifapentine; MMT= methadone maintenance treatment; BPN/NLX= buprenorphine/naloxone; OAT=opioid agonist treatment; ART= antiretroviral therapy; HCV= hepatitis C virus.

Part C:

A two-arm **preference trial** (no MAT, and methadone) of prisoners with opioid use disorders who are not or are currently being treated for TB and/or HIV, and are about to transition to the community and need to continue their treatment post-release. Patients may or may not be returning to Klang Valley and within 25 km of our research site. We anticipate enrolling 25-50 participants per arm.

Once consented, study participants will be provided an informed decision-making aid that will help them decide if medication-assisted treatment, specifically Methadone, is best for them. Participants will also have the option not to enroll in medication-assisted treatment.

[figure not shown]
Informed decision-making aid:

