- 1) Selecting experts in the field (HIV, TB, Substance abuse) who will serve as members of the board. If funded, we will select two U.S. and one Malaysian experts to serve on the DSMB. As in other NIDA trials, we will work with NIDA staff to select these individuals. Individuals from NIDA will be responsible for the final invitation to participate on the Board. During the first six months of the study, while final implementation is being conducted, the DSMB will convene to go over their charge, examine the guidance set forth by the study team and to question the PI and biostatisticians about pre-defined endpoints. Once these outcomes and stopping rules are defined, the Board will reconvene at regularly scheduled times to assess outcomes.

Defining stopping rules. For Aim 1, part B, we will be examining completion and tolerability of two LTBI prevention strategies. The study is not powered to reduce development of active TB, but to establish safety in prisoners who have high prevalence of HCV infection. Tolerability (discontinuation from study medication) will be the primary outcome. All discontinuations will be reviewed by the PI and the team. Death will be brought to the DSMB within 24 hours if medication related (though most deaths are related to TB itself). If the discontinuation rate is 3-fold higher in either group, either in the interim analysis when 50% is enrolled or at any time within study assessment, the study will be stopped for safety purposes and a press release will be made. For Part B, we anticipate a difference between the control group and the two intervention groups of about 40%.

- 2)
- 3) Assessment of possible adverse consequences of the various interventions. No specific guidance is available for DSMBs for these kinds of interventions; however, we have considerable experience with CHRP, Project PLUS, Project TRUST, Project CONNECT, Project BEST and other community research studies to provide a specific plan. In fact, in order to collect information about the "safety" of the intervention, we intend to hire a research assistant to gather safety information from three independent sources. These include the weekly study meeting where all active participants are discussed, daily conversations with the Health Educators and weekly conversations with the subject

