
Part B: In CDC's original non-inferiority trial of 26H v 12HR, treatment completion differed significantly (67.0% v 82.1%); however, there were no HIV+s (and therefore no ART prescribed)

and HCV infection was <3%. Therefore tolerability for a longer exposure to 26H may decrease completion further. We will compare the proportion completing TB preventive therapy (no adverse side effects) for the two groups and control for any confounders that may differ after randomization. Using an alpha=0.05 and power=0.8 and a 20% difference (most conservative), we would need 118 per arm. We hypothesize, however, that 26H will be tolerated even less based on studies of IPT hepatotoxicity in a RCT of isoniazid in prisoners (21% in with HCV)⁴² and HCV+ patients (correlated with longer IPT exposure).⁴³⁻⁴⁵ Thus, even increasing the difference in treatment completion to 20% (still conservative), the sample size would need to be 164. Thus, we will conservatively enroll 177 per arm or 354 patients total. We will analyze the data two ways, including ITT as a difference in proportion of treatment completion used in RCTs. In order to discern factors associated with differences in treatment completion, we will treat the entire recruited sample as a cohort and using Cox regression, examine time to treatment discontinuation between the two groups using Cox Proportion Hazards as well as examine the independent factors associated with treatment discontinuation (e.g., being on ART, HCV status, baseline AST/ALT, CD4 strata, etc).

Part C: Eligibility will be having no TB disease, TB disease or LTBI, on TB medications that must be completed after release, and meet pre-incarceration DSM-V criteria for opioid dependence. We will compare a control group of prisoners choosing no OAT and compare them to OAT patients. Even though we anticipate 15-20% attrition, we will count missing=failure to be conservative and will censor the data based on the mid-point between the last and the missed visit. The primary outcome will be the proportion completing treatment for active or LTBI. Secondary analyses will compare Kaplan Meier curves using Cox proportion hazards and time to discontinuation. TB treatment adherence will also be measured using MEMS caps and analyzed as we have done previously in TB patients in Ukraine.

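### Part B's 3-fold safety stop does not restrict discontinuation by cause, exposure time or event count, so it barely responds to excess 12HR toxicity in mature data and can fire by chance early; its 40% sentence does not describe Part B.

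*Combined protocol and SAP*

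**What the plan says.** Section V.11 (*Defining stopping rules*) says Part B is not powered for active TB but is meant to establish safety where HCV is common. It names the endpoint: "Tolerability (discontinuation from study medication) will be the primary outcome". The scheduled trigger for the stop is worded: "If the discontinuation rate is 3-fold higher in either group, either in the interim analysis when 50% is enrolled". The rule is not confined to that look, because the sentence goes on to cover unscheduled looks too, and to state the consequence, which includes a press release. The paragraph does not say whether the rate is a proportion or per person-time. It gives no common follow-up time, no minimum number of events and no confidence bound.

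Section V.3 (Part B) sets the arms as 12HR for 12 weeks and 26H for 26 weeks, and lists the reasons for stopping drug: "Premature treatment discontinuation will occur for any DAIDS Grade 4 toxicity, patient refusal to continue, or pregnancy (women only"). Section V.10 (*Monitoring Adverse Side Effects*) gives a different individual stop, on liver-test limits and on Grade 3 or higher neuropathy.

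The plan expects more non-completion on 26H. Completion from the earlier large trial is 82.1% on 12HR, against 69.0% on 26H in Section V.3 and 67.0% in Section V.12. Section V.12 bases the sample size on a 20% difference. The stopping-rule paragraph, however, ends: "For Part B, we anticipate a difference between the control group and the two intervention groups of about 40" per cent.

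**The concern.** The safety question special to Part B is whether adding rifapentine raises liver toxicity in prisoners with HCV. A rule that adds refusals to toxicity, and then asks for a 3-fold excess over the arm expected to lose more patients, is a poor instrument for that question. A shorter course that cuts refusals can offset a real rise in toxicity. Conversely, refusals on 26H can push the rule towards a stop labelled as safety.

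Because the rule also runs at any time, on arms with unequal course lengths, small early counts can cross a ratio of 3. The DSMB would hold a rule that is insensitive when data are mature and unstable when they are sparse, beside an anticipated effect that belongs to some other comparison.

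**Working it through.** **Plan's own figures.** The plan states no operating characteristic for the stop. The nearest figures are the Section V.12 sample sizes for 20% (alpha 0.05, power 0.80): 118 per arm, then 164. With n = [z_a√(2p̄q̄) + z_b√(p₁q₁ + p₂q₂)]² / (p₁ − p₂)²:

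- An absolute 20-point difference needs most at 40% v 60%: 97 per arm two-sided, 107 with continuity correction. Neither 118 nor 164 is reached.
- 20% relative to 69.0% (69.0% v 82.8%) gives 118 one-sided without correction and 164 two-sided with correction.

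The plan's numbers therefore fit a relative 20% better than an absolute one, and the text does not say which is meant.

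**Threshold on completed courses.** Taking discontinuation as 100% minus completion:

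- 12HR: 100 − 82.1 = 17.9%.
- 26H: 100 − 69.0 = 31.0%, or 100 − 67.0 = 33.0%.
- Expected ratio, 26H to 12HR: 31.0/17.9 = 1.73; 33.0/17.9 = 1.84.
- Stop against 12HR: 3 × 31.0 = 93.0%; 3 × 33.0 = 99.0%.
- Stop against 26H: 3 × 17.9 = 53.7%.

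**Chance of a stop against 12HR at the half-way look.** Half of 354 is 177, about 88 per arm. Exact binomial probability that the 12HR count is at least three times the 26H count:

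| 12HR discontinuation | 26H 31.0% | 26H 33.0% |
|---|---|---|
| 38.9% (17.9 plus an assumed 21 points of extra toxicity) | 0.0002 | 0.00004 |
| 60% | 0.017 | 0.007 |
| 90% | 0.44 | 0.30 |

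**Dilution (assumed figures).** Let 26H lose 5% to liver events and 26% to other causes (31%), and 12HR lose 15% and 13% (28%). Liver toxicity has tripled, yet the ratio is 28/31 = 0.90.

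**Equal exposure.** With a constant hazard (assumed), 26H discontinuation by week 12 is 1 − 0.690^(12/26) = 15.7% or 1 − 0.670^(12/26) = 16.9%. Three times these is 47% to 51%. With 12HR at 38.9% and 88 per arm, the chance of a stop is then 0.28 or 0.20. Tripling the 26H hazard per person-week corresponds to 40% to 43% on 12HR.

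**The any-time clause.** Simulation of 354 patients enrolled evenly over 104 weeks (assumed), constant hazards, 1000 runs. Share of runs in which the ratio crosses 3 against 12HR at some point:

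| Ratio judged from | No excess (69.0% v 82.1% completion) | 12HR discontinuation 38.9% |
|---|---|---|
| 1 event | 61% | 88% |
| 4 events | 28% | 73% |
| 10 events | 5% | 57% |
| 20 events | 0.1% | 22% |

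**The 40% sentence.** Absolute differences in the plan are 82.1 − 69.0 = 13.1, 82.1 − 67.0 = 15.1, and 20 if the design difference is in points. As relative cuts in discontinuation, 13.1/31.0 = 42% and 15.1/33.0 = 46%. If 40 points in favour of 12HR were meant, 26H would be at 17.9 + 40 = 57.9%, and 57.9/17.9 = 3.2 meets the stop. On the relative reading the ratio is 1.73 to 1.84 and does not. Neither reading supplies a control group and two intervention groups.

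**The case against.** Several stronger readings are tempting, and the documents do not support them.

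- *The rule can never fire against 12HR.* Both 93% and 99% are below 100%, and they compare finished courses of unequal length. At equal exposure, or early under the any-time clause, the rule can fire. If 26H discontinuation proved to be 10%, the threshold would be 30%.
- *The threshold exceeds 100%.* Setting 26H 20 points below 82.1% gives 3 × 37.9 = 113.7%, but this treats 20% as absolute, which does not reproduce the plan's sample sizes.
- *The rule is blind to toxicity.* Toxicity stops are counted; they are diluted, not invisible. Isoniazid hepatotoxicity is also a concern on 26H (Section V.12 cites 21% with HCV), so a stop against 26H could be a genuine safety stop.
- *Releases alone could stop the trial.* Section V.3 does say that "the major factor contributing to treatment non-completion is release from prison and hepatotoxicity", but of past preventive therapy. Part B requires at least 6 months of sentence remaining, and its list of discontinuation reasons omits release. Refusal is the better example.
- *This is the DSMB's only quantitative stop.* Part of Section V.11 was not in the text reviewed, and the section expects the DSMB to meet over endpoints and stopping rules.
- *The 40% is the benchmark for the stop.* The plan calls it only an anticipated difference. Its wording resembles Part C as described in Section V.1 (no OAT against OAT split into two drugs).

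The plan also has the team review every discontinuation, and takes medication-related deaths to the DSMB within 24 hours. These are real protections, but the passages available set no between-arm criterion for toxicity. Lastly, no restriction by cause is an inference: the plan never says all-cause, and Section V.12 glosses completion as free of adverse effects. It is the natural reading of Sections V.3 and V.11 together.

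**Conclusion.** The point holds in this form: the stop does not isolate toxicity, and it has no time basis or minimum count. On the plan's completed-course figures it is practically unable to detect excess 12HR toxicity. In early data it can fire against 12HR with no excess toxicity at all. The three-group sentence fits no reading of Part B and is unreconciled with the design difference in Section V.12.

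The completed-course thresholds follow directly from the plan's completion figures, if non-completion stands in for discontinuation. The probabilities rest on assumptions: 21 points as the size of extra toxicity, constant hazards, and even enrolment over 104 weeks. Changing these would move the early-look percentages, but not the 93% to 99%. The text should be corrected before the DSMB works from it.

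**What to change.** 1. In Section V.11, base the between-arm safety comparison on discontinuations for any protocol-defined toxicity, including DAIDS Grade 4 events as well as liver and neuropathy stops. The individual stopping criteria in Sections V.3 and V.10 differ and must be reconciled first. State a common exposure time and a minimum number of events before the ratio is judged. Report total discontinuation to the DSMB separately, as tolerability.
2. Remove the 40% sentence, or correct it to the 26H v 12HR contrast so that it agrees with the difference in Section V.12, and say whether that difference is absolute or relative.

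The cost is wording in the monitoring plan, since every discontinuation is already reviewed. The downside is that fewer events feed the rule, which is why the minimum count is needed. With an assumed 5% true toxicity in both arms and 88 per arm, a bare 3-fold rule fires falsely about 9% of the time in each direction, or 18% in all, at a single look.

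### The Part B 3-fold stopping rule can be applied at any time without an evidence threshold, a schedule or a defined rate, so early or repeated checks can meet it by chance

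*Combined protocol and SAP*

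**What the plan says.** The rule stands in Section V, item 11 (Data and Safety Monitoring Plan), in the paragraph on defining stopping rules. It applies under this condition: "discontinuation rate is 3-fold higher in either group, either in the interim analysis when 50% is enrolled or at any time within study assessment". What follows is mandatory: "the study will be stopped for safety purposes and a press release will be made". The same paragraph names discontinuation from study medication as the primary tolerability outcome and adds: "All discontinuations will be reviewed by the PI and the team".

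On process, item 11 has the DSMB meet in the first six months to go over its charge and the pre-defined endpoints. It continues: "Once these outcomes and stopping rules are defined, the Board will reconvene at regularly scheduled times to assess outcomes". No meeting interval is given. Part of the DSMB text was not available for this review.

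Section V, item 3, Part B gives the exposure: "participants will be provided 12HR weekly (12 weeks) and 26H daily (26 weeks) as directly observed therapy". It lists the grounds for stopping treatment, "Premature treatment discontinuation will occur for any DAIDS Grade 4 toxicity, patient refusal to continue, or pregnancy" (the last for women only), and sets patient monitoring: "Every 4 weeks, patients will be monitored for AST/ALT, adverse side effects and pregnancy". Section V, item 12 plans 177 per arm, 354 in total.

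**The concern.** A ratio of two small counts is unstable. Three discontinuations against one is a 3-fold difference, and so, on a literal reading, is any count against zero. A mandatory rule that can be applied at any time can therefore be met in the first months, when only a handful of events exist, and each further check gives chance another opportunity.

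The rate is also undefined. The event is identified, but the text does not say whether the rate is a proportion of patients or a rate per unit of treatment time, or over what window. With courses of 12 and 26 weeks, that choice changes the answer. Nor is it clear whether refusal and pregnancy count, so a stop declared on safety grounds may not reflect toxicity.

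At stake is the Part B comparison itself. A stop on a few chance events, followed by a press release, leaves the question unanswered, and no later analysis can repair that.

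**Working it through.** **Plan's own figure.** The available text states no false-stop or detection probability for this rule, so there is none to reproduce.

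**Step 1: one comparison, no true difference.** With equal arms, each of m discontinuations is equally likely to fall in either arm, so k ~ Binomial(m, 0.5). The rule is met if k ≥ 3(m−k) or (m−k) ≥ 3k.

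| Events m | Splits meeting the rule | Probability | If each arm must have an event |
|---|---|---|---|
| 4 | 10/16 | 62.5% | 50% |
| 8 | 74/256 | 28.9% | 28.1% |
| 12 | 598/4,096 | 14.6% | 14.6% |
| 20 | 43,400/1,048,576 | 4.1% | 4.1% |

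This step needs no assumption about accrual or risk.

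**Step 2: the one look the plan names.** Half of 354 is 177, or about 88 per arm. With a proportion as the rate, full follow-up and equal true risk, the exact chance of a ratio of 3 or more is 18% at 5% risk, 4.0% at 10%, 0.3% at 18% and below 0.01% at 33%. The cited completion figures in Section V, item 3 imply non-completion of 100 − 82.1 = 17.9% and 100 − 69.0 = 31.0%, so the planning range falls where this look is reliable. With incomplete follow-up it is less so: at 20% risk in both arms and events spread over the course, simulated false stops are 0.5-9% across accrual of 52-156 weeks.

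**Step 3: repeated checks, no true difference.** From the documents: 177 per arm, courses of 12 and 26 weeks. Assumed: uniform accrual over 52, 104 or 156 weeks; equal risk of 10-30% per course; crude proportions; checks until 26 weeks after accrual ends. The first two result columns have events spread over the course. The last has all events in the first 8 weeks.

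| Checks | Rule met at least once, spread events | Same, each arm must have an event | Early events |
|---|---|---|---|
| Six-monthly | about 2-52% | 2-30% | 0-36% |
| Quarterly | about 37-75% | 28-39% | 3-65% |
| 4-weekly | about 79-94% | about 44-59% | 57-90% |

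The first and last columns count a zero in one arm as meeting the rule.

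**Step 4: the definition of rate.** If the risk per course is equal and the hazard constant, the weekly rates differ by 26/12 = 2.17 purely because the courses differ in length. At 18% risk per course, 104 weeks of accrual and six-monthly checks, the rule is met in 20% of trials using proportions and 46% using person-time.

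**Step 5: what an evidence threshold does.** With equal arms, the exact two-sided p for m against 0 is 2 × 0.5^m: 0.016 at 7 v 0, 0.008 at 8 v 0, 0.002 at 10 v 0. For 3 v 1 it is 2 × 5/16 = 0.625. Adding p<0.01 to the 3-fold ratio therefore blocks 3 v 1 but still stops at 8 v 0. Simulated with crude proportions, spread events and quarterly or six-monthly checks:

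| Scenario | Current ratio alone | 3-fold plus p<0.01 | 3-fold, Kaplan-Meier, at least 20 events |
|---|---|---|---|
| No true difference | about 2-75% | about 1-9% | 0-3.9% |
| True 10% v 1% | 98-100% | about 88-94% | 44-54% |
| True 15% v 5% | about 62-97% | about 53-78% | about 60-73% |

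A hard minimum of 20 events gives few false stops but cannot stop at 19 v 0, where p = 2 × 0.5^19, about 0.000004. That is why it is not recommended.

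**The case against.** The strongest defence has three parts. First, the DSMB was to settle the rules, and part of its section was not available, so a fuller rule may exist. This stands as a limit on certainty. It does not remove the need to reconcile that rule with a sentence that makes the stop mandatory. Second, Part B is meant to establish safety in prisoners with a high prevalence of HCV, so an over-sensitive rule may be deliberate. That is legitimate, but the choice should then be made with its false-stop probability in view. Third, the look at 50% enrolment works well at the cited risks. It does, and the problem is confined to the early and repeated checks.

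Four stronger readings are tempting and unsupported.

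- A reader might infer that the trial would almost always stop by chance. The 79-94% figure assumes a between-arm comparison every 4 weeks and counts zeros. The 4-week interval in the plan is for monitoring patients.
- A reader might infer that the 50% look is itself unsound. Step 2 shows otherwise at 18-33% risk, if the rate is a proportion and follow-up is similar between arms.
- A reader might infer that the rule systematically favours one regimen. At the 50% look with true risks of 30% v 10%, it fires in 64-86% of trials if 12HR is worse and 21-43% if 26H is worse when events are spread, but in 53-54% either way when events are early. The direction depends on timing that the documents do not fix.
- A reader might infer that refusal and pregnancy certainly count. Item 3 lists them as grounds for stopping treatment, but item 12 links completion to the absence of adverse effects. The text is ambiguous.

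**Conclusion.** The concern holds for early and repeated application of the rule and should be fixed; confidence is moderate. The exact split probabilities are firm. The trial-level figures, about 37-75% with quarterly and 2-52% with six-monthly checks, rest on assumed accrual, risk, event timing and schedule, and on counting a zero in one arm as 3-fold. Their width is itself informative: because the schedule and the rate are unstated, the rule's behaviour cannot be determined from the plan. The safeguards for individual patients (4-weekly monitoring in item 3, monthly review in item 10, review of every discontinuation in item 11) are separate and unaffected.

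**What to change.** Amend the stopping-rule paragraph and the DSMB charter so that they agree:

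1. Replace the any-time clause with the 50% look plus scheduled DSMB meetings, and state the schedule.
2. Keep the 3-fold ratio, but make it binding only when the difference also passes a stated evidence threshold, for example exact two-sided p<0.01. Have the DSMB review any 3-fold ratio that falls short of it.
3. Define the denominator and time window of the rate, how unequal or incomplete follow-up and zero counts are handled, and which discontinuations count.
4. Tabulate false-stop and detection probabilities for the chosen schedule, including low-event cases such as 10% v 1%.

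The table should also show what the definition of rate implies. Under a full-course definition, an equal weekly risk that gives 20-30% on 26H gives 9.8-15.2% on 12HR, about a 2-fold difference with no difference in weekly risk.

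The cost is a short amendment and a simulation table, with no added patients or procedures. The downside is fewer automatic stops on a few early events: detection of a true 15% v 5% falls from about 62-97% to about 53-78%. Early protection then rests on the individual reviews and patient-level stops already in Section V, items 3, 10 and 11.
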